An adequate respiratory sample (defined in the primary study) to determine the microbiological etiology of the pneumonia is to be collected within 36 hours of randomization, although all attempts should be made to obtain the specimen as close as possible to when the diagnosis of pneumonia is made. Note: Any time a BAL/non-bronchoscopic BAL or protected specimen brush (PSB) is performed to collect a respiratory microbiological sample, then a PK sample should also be collected to determine ASN-1 and ASN-2 levels to derive blood to ELF ratio, and to measure *S. aureus* toxins.

While hospitalized, randomized subjects will be monitored daily for up to 21 days for pneumonia resolution or recurrence, and the occurrence of other *S. aureus*-associated infections. If a subject's clinical symptoms of pneumonia improve such that no further antibiotic therapy is required, or if the pneumonia persists requiring a change in antibiotic therapy, then all attempts will be made to collect an adequate respiratory specimen.

All randomized subjects will undergo a study visit on Day 22 (+2 days) for assessment of pneumonia. An adequate respiratory specimen should be obtained from subjects who remain ventilated and non-ventilated subjects who are able to produce sputum.

A Follow-Up Visit will occur on Day 28 (+2 days) to assess mortality. This visit may be conducted via telephone if the subject is no longer hospitalized.

For subjects who remain hospitalized between Days 40 and 90 at the institution where they receive study treatment, the Follow-Up Visit will be performed on the day of discharge.

All randomized subjects will return for a Safety Visit on Day 90 ( $\pm 7$  days) (if the subject is unable to return to the site, this visit may be conducted by telephone). Subjects who discontinue the study prior to Day 22 will undergo an Early Termination Visit. The end of the study will occur upon completion of the last study visit (e.g., Day 90) visit by the last subject.

Safety assessments for this study will include adverse event (AE) monitoring, clinical laboratory assessments (including chemistry, hematology, coagulation, and urinalysis), physical examinations, vital sign measurements, 12-lead electrocardiograms (ECGs), chest X-rays and/or thoracic computed tomography (CT) scans, and the determination of the presence of ASN-1 and ASN-2 anti-drug antibodies (ADAs). Additional safety assessments may be performed throughout the duration of the study if clinically indicated.

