Procalcitonin testing will be performed at the Randomization Visit (Day 1 pre-dose), and on Day 22 or Early Termination (if applicable).

Blood samples will be obtained for the measurement of ASN-1 and ASN-2 in serum. Blood samples for PK analysis will be collected immediately following the completion of the second infusion (+15 minutes) and at 6 hours ( $\pm 4$  hours) and 24 hours ( $\pm 6$  hours) post-dose following the second infusion. In addition, a PK sample will be obtained from all subjects on Days 4 ( $\pm 1$  day), 7 ( $\pm 1$  day), 14 ( $\pm 2$  days), and 22 (+2 days) of the Monitoring Period. Additional PK samples will be collected on the day of discharge (if discharge occurs between Day 40 and Day 90), on Day 90 (if hospitalized or if the subject is able to return to the clinic), or Early Termination (if applicable).

Blood samples obtained for ADA and PK analysis purposes will also be used to assess the amount of pre-existing anti-*S. aureus* toxin antibodies and the toxin neutralizing titer of the serum sample prior to and after randomization. Only antigen-specific antibody titers will be determined, and no genetic information will be extracted from these blood samples. Blood samples will be destroyed following the completion of all *S. aureus* anti-toxin antibody analyses.

BAL fluid obtained during the procedure to assess the baseline pneumonia pathogen (within 36 hours of randomization), and in subjects who participate in the BAL PK sub-study, will be analyzed for the presence of *S. aureus* toxins. No genetic information will be extracted from these samples, which will be destroyed following the completion of this analysis.

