## 7. EFFICACY ASSESSMENTS

### 7.1. Primary Efficacy Endpoint

The primary efficacy endpoint is the resolution of *S. aureus* pneumonia in the microbiologically evaluable modified intent-to-treat (mMITT) Population up to, but not including, Day 22.

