### 7.3. Microbiological and Clinical Assessments

#### 7.3.1 Microbiological Assessment

In the primary study, ETA specimens will be collected for culture during the Screening/Enrollment Period to determine the degree of *S. aureus* colonization. Additional respiratory specimens may be collected for culture throughout the Monitoring Period or at Early Termination (if applicable) if clinically indicated according to standard of care.

If, as part of routine standard of care, additional respiratory and/or other microbiological specimens are collected for culture during the study, results will be documented within the electronic case report form. As described within the study laboratory manual, bacterial isolates recovered from these specimens that are deemed pathogens by the Investigator (if retained and available at the study site local microbiology laboratory) will be sent to a central microbiology laboratory for confirmation of pathogen identification (all isolates) and susceptibility testing (*S. aureus* isolates only).

For a Sponsor diagnosis of *S. aureus* pneumonia, an adequate respiratory specimen culture that is positive for *S. aureus* must be obtained within 36 hours from randomization.

- For intubated subjects, a respiratory specimen obtained by BAL, non-bronchoscopic BAL, or PSB will be considered an adequate respiratory specimen;
- For extubated subjects, an adequate expectorated/induced sputum specimen is defined as <10 squamous epithelial cells and >25 PMNs/100× field; and
- Adequate respiratory specimens will undergo either semi-quantitative or quantitative culture in accordance with the local laboratory standard procedure. For each subject, the sampling and testing method should be consistent for microbiological diagnosis of both pneumonia and its resolution.

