#### **Microbiologically Evaluable Modified Intent-to-Treat (mMITT) Population**

The mMITT Population includes those subjects in the MITT Population that have confirmation by an adequate respiratory sample of a microbiological etiology of pneumonia as *S. aureus*, either MSSA or MRSA, without recovery of any other bacterial pathogens

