## 10. APPENDICES

### 10.1. Schedule of Procedures for Sub-Study

Study Period	Random-ization	Treatment	Monitoring Period			Follow-Up Period			ET
Study Day	Day 1 Pre-dose	Day 1	Day 2/3 j (BAL PK Sub-study)	Days 2 to 21 k	Day 22 (+2 days)	Day 28 (+2 days) l	Days 40 to 89 m	Day 90 (±7 days) Safety Visit n	Unsched o
Study Procedures									
Inclusion/exclusion criteria	X p								
Medical history a	X								
Antibiotic/medication history a	X								
Physical examination b	X			X	X		X	X	X
Vital signs c	X	X	X	X	X		X	X	X
Pregnancy test d	X				X				X
Clinical lab assessments e	X			X	X				X v
Urinalysis	X			X q	X				X v
Procalcitonin (central lab)	X				X				X
Ventilator device status	X	X	X	X	X	X	X	X	X
Chest X-ray/thoracic CT scan	X		X	X r	X				X r
Nasal swab for culture	X								
Collection/culture of respiratory microbiological specimens f		X		X s	X t				X t
Collection/culture of additional microbiological specimens g				X	X				X
Clinical assessment of signs/symptoms of pneumonia	X	X	X	X	X				X
Other S. aureus infection assessment	X	X	X	X	X				X
Randomization	X								
Blood collection for ADA and anti- S. aureus toxin antibodies	X			X u	X		X	X	X
12-lead ECG	X				X		X	X	X
Survival and discharge disposition					X	X	X	X	X

Study Period	Random-ization	Treatment	Monitoring Period			Follow-Up Period			ET
	Day 1 Pre-dose		Day 1	Day 2/3 i (BAL PK Sub-study)	Days 2 to 21 k	Day 22 (+2 days)	Day 28 (+2 days) l	Days 40 to 89 m	Day 90 (±7 days) Safety Visit n
Study Procedures									
Study drug administration h		X							
BAL for PK (Optional)			X						
Blood collection for PK sampling and anti- S. aureus toxin antibodies		X v	X w	X x	X x		X x	X	X
Track days on ventilator from randomization		X	X	X	X		X	X	X
Track days in ICU (or other observation area)		X	X	X	X		X	X	X
Concomitant medications i	X	X	X	X	X		X	X	X
Adverse event assessment	X	X	X	X	X		X	X	X

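### In the Appendix C treatment sub-study, nothing requires the specimen that decides entry to the primary mMITT population to be taken before study drug

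*Protocol*

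**What the plan says.** All references are to protocol Appendix C unless stated.

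- **Primary population.** Section 7.1 places the primary endpoint "in the microbiologically evaluable modified intent-to-treat (mMITT) Population up to, but not including, Day 22". Section 9.3 compares the proportion resolved in that population only.
- **Entry rule.** Section 9.1 requires "confirmation by an adequate respiratory sample of a microbiological etiology of pneumonia as" *S. aureus*, "without recovery of any other bacterial pathogens". E-mMITT drops the last condition. Neither definition gives a time window or a pre-dose condition.
- **Timing in the text.** Section 3 says the sample "to determine the microbiological etiology of the pneumonia is to be collected within 36 hours of randomization" and adds that staff should try to take it as near to diagnosis as they can; footnote f of Section 10.1 repeats both. Section 7.3.1 says that, for the Sponsor's diagnosis of *S. aureus* pneumonia, the positive culture "must be obtained within 36 hours from randomization".
- **Timing in the schedule.** In Section 10.1 the row "Collection/culture of respiratory microbiological specimens" has its first mark under Treatment (Day 1). The Day 1 pre-dose cell is blank.
- **Label.** Section 3 refers to the "procedure to assess the baseline pneumonia pathogen (within 36 hours of randomization").
- **Dosing.** Study drug follows randomization on Day 1, on top of standard-of-care therapy (Section 3).
- **MITT.** This population rests on the qualifying endotracheal aspirate culture and receipt of study drug, so it does not depend on this specimen (Section 9.1).

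**The concern.** A culture that defines an analysis population should be fixed before treatment can act on it. Here it need not be. A subject dosed on Day 1 and sampled a day later may by then have a negative culture, a second organism, or no adequate specimen at all. That subject leaves mMITT because of something that happened after randomization. If this happens at different rates in the two arms, the subjects left in mMITT are no longer comparable by randomization.

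Two lesser consequences follow. The Day 22 microbiological outcomes (Section 7.3.3.3) are judged against the baseline pathogen, so they inherit the ambiguity. Section 3 also has the same lavage fluid tested for *S. aureus* toxins, and a result obtained after an anti-toxin antibody cannot be read in the same way as one obtained before it.

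**Working it through.** **Plan figure.** There is none to reproduce. Section 9.2 says that no formal sample-size assessment was made for the sub-study.

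**Is pre-dose collection required anywhere?** No.
- The 36-hour wording gives no direction, so it admits specimens before or after randomization.
- The schedule points to Treatment Day 1. Main protocol Section 6.4 introduces that day's procedures as following study drug, but its list includes the dosing step itself, so the column is not strictly post-dose.
- The request to sample near diagnosis is an aim, not a condition of entry to mMITT.
- The SAP does not cover the sub-study. Its Section 7.4 baseline, for the parent study, is the last assessment before dosing.

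**Latest specimen.** Imaging may precede randomization by up to 24 hours (Section 4.1) and the specimen may follow it by up to 36 hours: 24 + 36 = 60 hours after the qualifying image.

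**Illustration of selection.** The documents give no inputs, so every value here is an assumption. Let p be the true resolution rate, equal in both arms; f the share of specimens taken post-dose; and q the share of those that have turned negative, all in subjects who go on to resolve. Then

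observed mMITT rate = (p - f·q) / (1 - f·q), with p = 0.60.

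| f | q, ASN100 / placebo | ASN100 | Placebo | Difference |
|---|---|---|---|---|
| 0.3 | 0.30 / 0.15 | 0.51/0.91 = 56.0% | 0.555/0.955 = 58.1% | about -2 points |
| 0.5 | 0.30 / 0.15 | 0.45/0.85 = 52.9% | 0.525/0.925 = 56.8% | about -4 points |
| 0.7 | 0.40 / 0.20 | 0.32/0.72 = 44.4% | 0.46/0.86 = 53.5% | about -9 points |

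**Equal loss.** Use x for the share of eventual resolvers whose culture has converted before sampling. The observed rate is p(1 - x) / [p(1 - x) + 1 - p]. With x = 0.10 in both arms, both rates are 0.54/0.94 = 57.4% and the difference is 0; only the numbers fall. With x = 0.10 on placebo and 0.30 on ASN100, the rates are 57.4% and 0.42/0.82 = 51.2%, a difference of -6.2 points.

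**How strong the assumptions are.** With q = 0.30 and p = 0.60, 0.30/0.60 = half of the eventual resolvers sampled post-dose must already be culture-negative. With q = 0.40 it is 0.40/0.60 = two-thirds.

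**Precision.** With 25 per arm, and even if every subject were *S. aureus*-only, the middle row leaves 25 × 0.85 = 21.3 and 25 × 0.925 = 23.1. The standard error of the difference is √(0.529·0.471/21.3 + 0.568·0.432/23.1) ≈ 0.15. A -4 point shift is about a quarter of that.

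**The case against.** The strongest reply is that the protocol aims at a specimen taken at about the time of diagnosis. Diagnosis and imaging are entry criteria and precede randomization, so 36 hours is a tolerance. That stands as intent. It does not stand as a rule, because no population definition uses it.

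Four stronger readings are tempting, and the documents do not support them.

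- **That the specimen must be, or is expected to be, taken after dosing.** The schedule mark suggests it, but the text allows pre-dose collection. The instruction to measure drug levels applies whenever a lavage or brush is done, including later specimens, so it does not show that this one is expected post-dose.
- **That ASN100's best early responders will be removed.** This needs an effect on culture within 36 hours, and none is documented. Main protocol Section 1.3 describes toxin neutralization only. Section 1.1 does say that leukocidins impair bacterial clearance by phagocytes, so an effect is conceivable. Who can be sampled is a separate route: extubated subjects need a qualifying sputum (Section 7.3.1), and early death may prevent sampling. Losing early deaths would push the bias the other way, so even its sign is not fixed.
- **That antibiotics bias the comparison.** They are background care in both arms. Equal clearance reduces the sample and leaves the difference unchanged. Stratification covers exposure up to randomization, but not the hours between randomization and the specimen.
- **That a baseline toxin endpoint is spoiled.** No objective in Sections 2.1 and 2.2 and no endpoint in Sections 7.1 and 7.2 uses a baseline toxin value. Clear labelling is enough.

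Part of the risk is already covered. Time to resolution of *S. aureus* pneumonia is also analysed in MITT and E-mMITT (Section 7.2), and E-mMITT keeps subjects with a second organism. The primary proportion has no such companion analysis.

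**Conclusion.** The point holds as a gap in timing and definition. Membership of the primary mMITT population can be settled after study drug, the specimen is nevertheless called baseline, and text, schedule and population definitions do not agree on when it is taken. Post-dose collection is permitted, not required.

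The size of any bias is unknown. The -2 to -9 points come from assumed inputs that give ASN100 twice the placebo conversion rate in every row. The figure is zero if loss is equal by arm, and it could be of opposite sign if the subjects lost are mainly those who do not resolve. It should not be quoted as an expected effect.

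The consequence is confined to the interpretation of an unpowered pilot of about 50 subjects. The main prevention trial is unaffected.

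**What to change.** 1. Reconcile Sections 3, 7.3.1 and 10.1 (including footnote f) so that the specimen is scheduled at the Day 1 pre-dose visit, without waiting for its result and without delaying dosing.
2. Record the specimen time relative to the first infusion and to antibiotics.
3. State the collection window in the mMITT and E-mMITT definitions in Section 9.1.
4. Prespecify two sensitivity analyses of the primary resolution proportion: in MITT, and in mMITT restricted to pre-dose specimens.
5. Label each lavage toxin result as pre- or post-dose.

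I would not restrict the primary mMITT itself to pre-dose specimens. If half were taken late, 25 × 0.5 = 12.5, so about 12 per arm at most would remain. As a sensitivity analysis, the restriction removes selection by study drug through the culture result by construction. It does not remove the effect of antibiotics given before the specimen, which should be stated as a limitation.

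The cost is protocol wording, one schedule cell, a recorded time and a little more analysis. The specimen is already required. The downside is a small pre-dose subset if many specimens are taken late.

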## 4. SELECTION OF SUB-STUDY SUBJECTS

### 4.1. Inclusion Criteria

Subjects must meet all of the following criteria at the Randomization Visit in order to be eligible for randomization into the sub-study:

1. Subject is currently hospitalized and enrolled in the Arsanis Protocol ASN100-201;
2. Subject is presumed to have *S. aureus* pneumonia as determined by heavy *S. aureus* colonization of ETA (defined as quantitative threshold of  $\geq 10^5$  CFU/mL or 3+ to 4+ by semi-quantitative culture);
3. Subject has both signs and symptoms supporting a clinical diagnosis of pneumonia per the Investigator and has an imaging study (chest X-ray or thoracic CT) supportive of the diagnosis of pneumonia; and
4. Subject is randomized within 24 hours of the imaging study supporting the diagnosis of pneumonia (see Criterion 3 above).

### 4.2. Exclusion Criteria

Subjects who meet any of the following criteria at the Randomization Visit will be excluded from participation in the sub-study:

1. Subject has a known and documented ETA culture showing heavy colonization with a non-*Staphylococcus aureus* organism (e.g., a Gram-negative organism)  
NOTE: Randomization should not be delayed while waiting for other culture results if heavy colonization with *S. aureus* has been confirmed.
2. Subject has been diagnosed with neutropenia (absolute neutrophil count  $< 500/\text{mm}^3$ );
3. Subject has a severe non-pulmonary source of infection which, in the Investigator's opinion, would interfere with the conduct of the study or jeopardize the subject's safety;
4. Subject has been previously exposed to ASN100 or ASN-1 or ASN-2, individually;
5. Subject has a known hypersensitivity to ASN100 or any of its excipients;
6. Subject has received any investigational product within 30 days prior to the Screening Visit (or 5 half-lives of the investigational product, whichever is longer);
7. Subject has, in the opinion of the Investigator, a high probability of death within 72 hours of randomization;
8. Subject is, in the opinion of the Investigator, not able or willing to comply with the protocol;
9. Subject has any condition that, in the opinion of the Investigator, would compromise the safety of the subject, the potential activity of the study drug, or the quality of the data; or
10. Subjects with a known history or current (suspected) diagnosis of cytokine release syndrome associated with the administration of peptides, proteins, and/or antibodies.  
NOTE: Subjects with a prior history of sepsis are not excluded.

## **5. SUB-STUDY TREATMENTS**

### **5.1. Study Medication**

Study medication (ASN100 or placebo) will be administered at the same dose and following the same preparation and administration procedures as per the primary study.

#### **5.1.1 ASN100**

ASN-1 and ASN-2 will be supplied in separate 10-mL vials as a sterile, colorless, clear solution for infusion with an extractable volume of 10 mL and a nominal mAb concentration of 20 mg/mL. Each vial will contain 200 mg of ASN-1 or 200 mg of ASN-2. ASN100 will be administered as separate infusions of 1800 mg ASN-1 and 1800 mg ASN-2 (9 vials of each to be pooled aseptically according to the Pharmacy Manual into separate infusion bags), each delivered over 50-60 minutes intravenously, either sequentially within a 3-hour window from the time of initiation of the first infusion to the completion of the second infusion, or simultaneously.

#### **5.1.2 Placebo**

Matched vials of ASN-1 placebo and ASN-2 placebo will be provided.

Placebo will be administered as separate infusions of 9 vials of ASN-1 placebo and 9 vials of ASN-2 placebo (vials to be pooled aseptically according to the Pharmacy Manual into separate infusion bags), each delivered over 50-60 minutes intravenously, either sequentially within a 3-hour window from the time of initiation of the first infusion to the completion of the second infusion, or simultaneously.

## **6. SUB-STUDY PROCEDURES**

Following randomization into the sub-study, procedures and assessments will follow those of the primary study, with minor modifications given the treatment aims of this sub-study. See Section [10.1](#) for a schedule of procedures for this sub-study.

## 7. EFFICACY ASSESSMENTS

### 7.1. Primary Efficacy Endpoint

The primary efficacy endpoint is the resolution of *S. aureus* pneumonia in the microbiologically evaluable modified intent-to-treat (mMITT) Population up to, but not including, Day 22.

### 7.2. Additional Efficacy Endpoints

- The time to resolution of *S. aureus* pneumonia in the modified intent-to-treat (MITT), mMITT, and expanded microbiologically evaluable modified intent-to-treat (E-mMITT) Populations;
- The time to resolution of all bacterial pneumonia in the MITT and mMITT Populations;
- The time to resolution of non-*S. aureus* pneumonia in the MITT and mMITT Populations;
- Duration of mechanical ventilation during the first 21 days post-randomization for subjects in the MITT, mMITT, and E-mMITT Populations;
- Length of ICU and hospital stay during the first 21 days post-randomization for subjects in the MITT, mMITT, and E-mMITT Populations;
- $C_{max}$ ,  $T_{max}$ , AUC, and  $t_{1/2}$  of ASN-1 and ASN-2 in serum following a single dose of ASN100 in the pharmacokinetic (PK) Population;
- 28-day all-cause mortality in the MITT, mMITT, and E-mMITT Populations;
- Development of ADAs to a single dose of ASN100;
- ASN-1 and ASN-2 levels in BAL fluid and blood to ELF ratio; and
- Incidence of other non-pulmonary *S. aureus* infections acquired following study drug administration up to the final study visit (e.g., Day 90, Early Termination, etc.) in the mMITT and E-mMITT Populations.

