#### **Expanded Microbiologically Evaluable Modified Intent-to-Treat (E-mMITT) Population**

The E-mMITT Population includes those subjects in the MITT Population that have confirmation by an adequate respiratory sample of a microbiological etiology of pneumonia as *S. aureus*, either MSSA or MRSA, with or without recovery of other bacterial pathogens.

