- An adequate respiratory sample to determine the microbiological etiology of the pneumonia should be collected within 36 hours of randomization, although all attempts should be made to obtain the specimen as close as possible to when the diagnosis of pneumonia was made. Note: Any time a BAL/non-bronchoscopic BAL or protected specimen brush (PSB) is performed to collect a respiratory microbiological sample, then a PK sample also should be will be collected to determine ASN-1 and ASN-2 levels to derive blood to ELF ratio, and to measure *S. aureus* toxins.
- If, as part of routine standard of care, additional non-respiratory microbiological specimens are collected for culture during the study, results will be documented within the eCRF; follow laboratory manual for which pathogens should be sent to central lab if isolates are available.

- h. Study drug will be administered in a double-blind manner. Subjects will receive ASN100 or matching placebo via 2 IV infusions over a duration of approximately 50 to 60 minutes per infusion. Both ASN100 and placebo will be administered as 2 separate infusions (either sequentially or simultaneously). The last infusion will be completed within 5 hours from initiation of drug preparation in the pharmacy.
- i. All prior medications received by the subject within 14 days prior to study drug administration and any concomitant medications used throughout the duration of the study will be recorded in the source documents and on the appropriate eCRF.
- j. Procedures are to be performed 48 hours ( $\pm 36$  hours) post-dose on approximately Day 2 or Day 3, depending on time of study drug administration, for those subjects participating in the BAL fluid PK sub study only or if BAL fluid is collected as part of a standard of care procedure for any subject at any other time post-randomization for any other reason.
- k. Procedures are to be performed daily (unless otherwise indicated) from Day 2 to Day 21 while the subject is hospitalized. For subjects participating in the BAL fluid PK sub study, procedures noted for the Day 2 visit only need to be performed 1 time.
- l. A follow-up visit will occur on Day 28 (+2 days) to assess mortality. This visit may be conducted via telephone if the subject is no longer hospitalized.
- m. For subjects who remain hospitalized between Day 40 and Day 90 at the institution where they receive study treatment, a follow-up safety visit will be performed on the day of discharge.

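### Appendix C lists time to resolution of non-*S. aureus* pneumonia in mMITT, but the mMITT definition leaves no such case at the index episode

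*Protocol*

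**What the plan says.** Appendix C section 7.2 gives three time-to-resolution endpoints for the treatment sub-study:

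- *S. aureus* pneumonia: "The time to resolution of *S. aureus* pneumonia in the modified intent-to-treat (MITT), mMITT, and expanded microbiologically evaluable modified intent-to-treat (E-mMITT) Populations".
- All bacterial pneumonia: "The time to resolution of all bacterial pneumonia in the MITT and mMITT Populations".
- Non-*S. aureus* pneumonia: "The time to resolution of non-*S. aureus* pneumonia in the MITT and mMITT Populations".

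Appendix C section 9.1 defines the two confirmed-etiology populations as subsets of MITT. Both require *S. aureus* to be confirmed by an adequate respiratory sample. mMITT adds "either MSSA or MRSA, without recovery of any other bacterial pathogens"; E-mMITT instead allows "either MSSA or MRSA, with or without recovery of other bacterial pathogens". MITT requires only receipt of study drug and heavy *S. aureus* colonization on endotracheal aspirate.

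The etiologic specimen is described in the notes to section 10.1: "An adequate respiratory sample to determine the microbiological etiology of the pneumonia should be collected within 36 hours of randomization". Sections 3 and 7.3.1 give the same 36-hour limit. The mMITT definition itself carries no time window.

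Section 9.3 mentions time to resolution only for *S. aureus* pneumonia and leaves other endpoints to be summarized by treatment group. The SAP, which is based on protocol Version 4.0, does not mention the sub-study, mMITT or E-mMITT.

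**The concern.** A pneumonia counts as non-*S. aureus* only if some other bacterium was recovered, and mMITT removes exactly the subjects in whom that happened. The population assigned to the endpoint and the definition of that population work against each other.

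Seven endpoints in section 7.2 name MITT, mMITT or E-mMITT, and five of them include E-mMITT. The two that omit it are the all-bacterial and non-*S. aureus* lines, where other pathogens matter most. That pattern suggests a drafting slip rather than a deliberate choice.

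If the text stands, the sub-study report would contain one table with no index cases. It would contain another that reproduces the *S. aureus* mMITT table under a different title, and a reader could take that as separate support. No primary conclusion is at risk.

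**Working it through.** The plan states no figure to reproduce, so the check is set logic on the definitions in Appendix C section 9.1.

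**Step 1. Classify the index pneumonia.** Let S mean that *S. aureus* was confirmed in the index respiratory specimen, and O that another bacterial pathogen was recovered from it. Split MITT into four groups:

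- a: S only
- b: S and O (mixed)
- c: O only
- d: no confirmed pathogen

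Then mMITT = a and E-mMITT = a + b, while MITT = a + b + c + d.

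**Step 2. Count index cases for each endpoint.** A mixed infection is counted under both the *S. aureus* and the non-*S. aureus* heading.

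| Endpoint | mMITT | E-mMITT | MITT |
|---|---|---|---|
| *S. aureus* (S) | a | a + b | a + b |
| All bacterial (S or O) | a | a + b | a + b + c |
| Non-*S. aureus* (O) | 0 | b | b + c |

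Group d cannot be assigned by pathogen. If it were presumed to be *S. aureus*, d would be added to the first two MITT cells and nothing else would change.

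**Step 3. Read the rows.**

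- Non-*S. aureus* in mMITT is 0 whatever the enrolment. In E-mMITT it is b, and in MITT b + c.
- All bacterial in mMITT is a, the same subjects with the same index episode as *S. aureus* in mMITT. The investigator's resolution criteria in section 7.3.3.1 are clinical and not tied to a pathogen, so the times are the same too.
- All bacterial in E-mMITT is a + b, which is again the *S. aureus* row. A mixed infection has one clinical resolution date.
- In MITT the all-bacterial and *S. aureus* rows differ by c, so the MITT version carries its own information.

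**Step 4. Can b and c exceed zero?** Yes. Exclusion criterion 1 in section 4.2 removes only subjects with a known, documented heavy non-*S. aureus* aspirate culture, and its note says randomization should not wait for other culture results. The documents give no rates, so b and c cannot be estimated.

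**Step 5. Does the time window matter?** If the mMITT restriction applies at any time, the 0 is absolute. If it applies only to the 36-hour specimen, an mMITT subject could later acquire another pathogen. Section 7.3.3.3 has categories for this (superinfection and new infection), and section 3 provides daily monitoring for resolution or recurrence. Such episodes could supply a few cases, but section 7.2 neither says that it covers them nor says when their clock would start.

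**The case against.** The strongest reply is the second reading in step 5. An index-specimen reading of mMITT is natural, because the etiologic specimen is tied to 36 hours. Under it, later non-*S. aureus* pneumonia in mMITT is possible and could also separate the all-bacterial result from the *S. aureus* one. This stands, so the 0 and the duplication are claims about the index episode only. It does not make the endpoint usable as written. Section 7.3.3.1 requires no new signs, symptoms or complications for resolution, section 7.3.3.3 counts a new pathogen as microbiological failure, and neither describes the resolution of a second episode.

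Three stronger readings are tempting, and the documents do not support them:

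- A reader might dismiss later infections because their clock could not start at randomization. No time origin is stated for any of the resolution endpoints; the post-randomization wording in section 7.2 belongs to ventilation and length of stay.
- A reader might infer that the objective in section 2.2 on all-bacterial and non-*S. aureus* resolution can no longer be addressed. That objective names no population, and MITT contains every mixed and every other-pathogen case (b + c). What is missing is a usable confirmed-etiology version.
- A reader might put E-mMITT into both lines. On the all-bacterial line that only moves the duplication, as the E-mMITT column in step 2 shows.

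The objection on materiality also stands: section 9.2 describes about 50 subjects with no formal sample-size calculation, and these are additional endpoints.

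**Conclusion.** The two sections conflict and need reconciling. For the index pneumonia, the non-*S. aureus* analysis in mMITT has 0 cases by definition, and the all-bacterial analysis in mMITT repeats the *S. aureus* mMITT result. The MITT analyses and the sub-study primary endpoint (*S. aureus* resolution in mMITT, section 7.1) are unaffected.

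The conclusion rests on three assumptions: the endpoints concern the index episode; resolution is judged by the clinical criteria of section 7.3.3.1; and a mixed infection counts as a non-*S. aureus* case. The third matters for the remedy rather than the defect: if mixed infections did not count, E-mMITT would also be empty on that line.

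Severity is low. The likely result is one empty table and one repeated table in a pilot sub-study, with no bias to any conclusion.

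**What to change.** In Appendix C section 7.2:

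1. Non-*S. aureus* line: replace mMITT with E-mMITT and keep MITT. State that a case is a subject whose adequate respiratory specimen within 36 hours of randomization grew a bacterial pathogen other than *S. aureus*, with or without *S. aureus*. Mixed cases are already in MITT, so no clause adding them is needed. E-mMITT contains all of mMITT plus the mixed infections, so the swap loses no case on either reading of the time window.
2. All-bacterial line: delete mMITT and keep MITT. Do not substitute E-mMITT.
3. If post-baseline non-*S. aureus* episodes are intended, say so and define their time origin.

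The cost is wording on two lines, plus one sentence if item 3 applies. The specimen is already scheduled, so items 1 and 2 need no new data or procedure.
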